10.3.2 Study Outcomes & Endpoints

Study measurements will be captured post each fraction of treatment. Assessments may include:

- Adverse events
- Dosimetry
- Physicist evaluation of imaging/packing
- Physician evaluation of imaging/packing
- Participant discomfort survey

There are two primary endpoints based upon dosimetry measurements in the bladder and the rectum. Each endpoint is the difference between D2cc dosimetry measurements obtained during periods 1 and 2 (fractions 2 and 3 under the 2x2 crossover structure). Additional assessments include data from periods 3 and 4 (fractions 4 and 5).

Additional endpoints include measurements over all periods for:

- Bladder and rectal dosimetry as measured by D0.1 cc and D1 cc.
- Participant reported discomfort
- Physicist evaluated imaging properties
- Physician evaluated imaging properties
- Physician evaluated use experience

10.4 Sample Size and Accrual

For this crossover study the primary comparison is based upon the 2x2 initial crossover portion. The primary endpoint is the difference of D2cc dosimetry measurements between periods 1 and 2 (fractions 2 and 3) for sequence arm A and sequence arm B based upon a two-sample comparison of the mean difference to the non-inferiority margin. Data from 51 patients treated at UVA with fraction 2 and 3 information, reported overall in Romano et al 2018¹⁹, with standard packing resulted in a mean (standard deviation) of 0.12 (1.56) and 0.10 (0.92) D2cc for the difference for bladder and rectal dosimetry, respectively. The

width of the 95% CI for the mean difference was 0.9 and 0.5 for bladder and rectal dosimetry, respectively. Based upon these measurements and clinical judgement, a non-inferiority margin of δ =(0.12+1.56=1.68) was chosen for this study.

Version Date: 11/16/2021

Justification for the sample size is based upon obtaining sufficient accrual to test the primary hypothesis that use of the hydrogel vaginal packing is non-inferior to standard packing methods in 1) bladder and 2) rectal dosimetry by more than a non-inferiority margin. Let $diff_A$ and $diff_B$ denote the differences between fractions.

The primary hypothesis to be tested is H_o : μ_{diffA} - μ_{diffB} $\geq \delta$ versus H_a : μ_{diffA} - μ_{diffB} $< \delta$, where the non-inferiority margin, δ =1.68, *each* for bladder and rectal, with a one-sided 2.5% level t-test. A sample size of 20 evaluable cervical cancer participants per arm achieves 94% power to detect non-inferiority using a one-sided t-test when the margin of non-inferiority is 1.68, the true difference between the means and the reference (standard) value is 0.12, and the assume population standard deviation is 1.56. Power is 96% if one uses the estimates for rectal dosimetry.

Adjusting for participants not satisfying the evaluable criteria (*section 10.3.1*), it is estimated that approximately 57 cervical cancer participants will need to be accrued to the study in order to test the primary study hypothesis. Each site may allow up to 10 oncologist and 4 physicists/dosimetrist to participate in completing the Physician and Physicist Assessments.

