10 STATISTICAL CONSIDERATIONS

10.1 Design

This is a two-center, stratified and randomized, four period, two arm crossover, noninferiority trial to demonstrate that BrachyGel Vaginal Hydrogel Packing System (hydrogel) is non-inferior to standard method vaginal packing (standard) in dose thresholds for D2cc (in Gy) for rectum and bladder by more than a non-inferiority margin of δ =1 Gy. Outcomes will be measured after each of 5 treatment fractions with results from the 1st fraction serving as the baseline measurement for each participant. D2cc measurements within organs varies between fractions as well as by participants, thus, each participant will receive both types of vaginal packing with order of packing type being chosen at random. Specifically, all participants will receive the standard method during the 1st fraction and then either sequence A (standard-hydrogel-standard-hydrogel) or sequence B (hydrogelstandard-hydrogel-standard) chosen at random, for the remaining four fractions. It is possible for participants to require less therapy during the final fraction (ie maximum therapy has been applied to the tumor), thus, the choice of ordering is limited to these two orderings to ensure that both packing types are administered to each participant with the primary assessment based upon fraction 2 and 3 data (ie, a two period, two treatment crossover).

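### The 10.4 test contrast is twice the packing effect, so its 1.68 margin means 0.84 Gy per fraction against 1 Gy in 10.1; the subtraction order is unstated and the printed power does not follow from the inputs

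*Combined protocol and SAP*

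**What the plan says.** Section 10.1 states the non-inferiority aim on D2cc for rectum and bladder "by more than a non-inferiority margin of δ =1 Gy". It assigns "either sequence A (standard-hydrogel-standard-hydrogel) or sequence B", the reverse alternation, after a common standard-packed first fraction. Section 6.1 agrees: hydrogel is used at fraction 3 in Arm A and at fraction 2 in Arm B.

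Section 10.4 compares fractions 2 and 3 "for sequence arm A and sequence arm B based upon a two-sample comparison of the mean difference to the non-inferiority margin". Its only definition of the quantities tested is "Let $diff_A$ and $diff_B$ denote the differences between fractions". The null hypothesis is that mean diffA minus mean diffB is at least δ, with δ = 1.68 for each organ, tested one-sided at 2.5%. Sections 10.3.2 and 10.6 add neither an order of subtraction nor a factor of one half.

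The planning data are 51 patients "with standard packing resulted in a mean (standard deviation) of 0.12 (1.56) and 0.10 (0.92) D2cc for the difference" (bladder, then rectum). The margin is the bladder mean plus one SD, 0.12 + 1.56 = 1.68. The plan then says: "A sample size of 20 evaluable cervical cancer participants per arm achieves 94% power to detect non-inferiority using a one-sided t-test", where "the true difference between the means and the reference (standard) value is 0.12, and the assume population standard deviation is 1.56". For the rectal estimates it prints 96%.

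**The concern.** In a two-period crossover, the between-arm difference of within-patient period differences estimates twice the treatment effect. A margin placed on that contrast is half as large per fraction. The plan does not mention this, and it prints a second margin elsewhere. A reader cannot tell what excess dose per fraction the primary test excludes.

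Three further points bear on the same calculation:

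- The direction of the test depends on a subtraction order that is never given.
- The assumed true difference of 0.12 comes from two standard-packed fractions, so it is not an estimate of a packing effect.
- The printed power looks wrong for the inputs printed beside it.

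At stake are the verdict on the primary endpoint, which could depend on which margin and scale are applied once data exist in an unblinded trial, and the adequacy of 20 evaluable participants per arm for bladder.

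**Working it through.** **Inputs.** From 10.4: 20 per arm, one-sided 2.5% t-test, δ = 1.68 for each organ, bladder 0.12 (SD 1.56), rectum 0.10 (SD 0.92). From 10.1: δ = 1 Gy. From 6.1 and 10.1: the sequences.

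**1. What the contrast estimates.** Let τ be hydrogel minus standard D2cc (higher is worse) and π the period effect, with no differential carryover. With diff = fraction 3 − fraction 2:

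- Arm A (standard, then hydrogel): mean diffA = π + τ
- Arm B (hydrogel, then standard): mean diffB = π − τ
- diffA − diffB = 2τ

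So 2τ < 1.68 is τ < 0.84 Gy per fraction. The two printed margins disagree on either scale: 1 Gy on τ is 2 Gy on the contrast, and 1.68 on τ would be 3.36.

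**2. Why the order matters.** With fraction 2 − fraction 3 in both arms, the contrast is −2τ, and rejection shows only τ > −0.84, which gives no protection against a higher hydrogel dose. With hydrogel − standard in each arm, τ cancels and only the period effect remains. Fraction 3 − fraction 2 is the one order of these that serves the stated aim with the alternative below δ.

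**3. Which SD is being used.** The plan reports that the "width of the 95% CI for the mean difference was 0.9 and 0.5 for bladder and rectal dosimetry, respectively". Check: 2 × t(0.975, 50) × SD/√51 gives 0.88 for SD 1.56 and 0.52 for SD 0.92. Both reproduce, so these are SDs of the unhalved within-patient difference and belong in the two-sample standard error.

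**4. Power on the stated inputs.** SE = SD × √(2/20); noncentrality = (δ − difference)/SE; noncentral t with 38 df; critical value 2.024.

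- Bladder: SE = 0.4933; (1.68 − 0.12)/0.4933 = 3.16; power **86.9%** (printed 94%).
- Rectum: SE = 0.2909; (1.68 − 0.10)/0.2909 = 5.43; power **99.96%** (printed 96%).
- The stated bladder inputs need 26 per arm for 94%; 25 per arm gives 93.4%.

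**5. The planning effect.** Using 0.12 as the contrast assumes τ = 0.06 Gy. For the test as written (2τ against 1.68, 20 per arm):

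| True τ (Gy) | Bladder, chance of claiming NI | Rectum |
|---|---|---|
| 0 | 91.3% | 99.99% |
| 0.06 | 86.9% | 99.9% |
| 0.12 | 81.2% | 99.8% |
| 0.84 | 2.5% | 2.5% |
| 1 | 0.5% | 0.1% |

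Simulation of 200,000 bladder trials per scenario, with a period effect of 0.12, gave 91.3%, 86.9%, 81.3%, 2.4% and 0.5%.

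**6. The verdict under each reading.** With the observed SD equal to the planning SD, the contrast must fall below δ − 2.024 × SE, halved to give τ. For a margin on τ, the rule is τ < δ − 2.024 × SE/2. Bladder as written: (1.68 − 0.9987)/2 = 0.34.

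| Reading of δ | Bladder power at τ = 0.06 | Observed τ must be below, bladder | Rectum |
|---|---|---|---|
| 1 on contrast | 41.2% | 0.00 | 0.21 |
| 1.68 on contrast (10.4 as written) | 86.9% | 0.34 | 0.55 |
| 1 on τ | 96.0% | 0.50 | 0.71 |
| 1.68 on τ | above 99.9% | 1.18 | 1.39 |

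**The case against.** - **The printed power can be matched.** Reversing the sign of the assumed difference and giving each organ its own mean-plus-SD margin yields 94.5% for bladder (margin 1.68, difference −0.12) and 96.3% for rectum (margin 1.02, difference −0.10). This is a fair observation, and it suggests that the missing subtraction order and the power figures may be linked. It does not rescue the text, which prints a positive 0.12 and sets 1.68 for each organ. It is also not proof of how the figures arose: a rectal margin of 1.00 with −0.10 gives 95.8%, which also rounds to 96%.
- **The scale is not settled by the SD check.** An unhalved SD is the right input on either margin scale, and a margin built from one patient's between-fraction difference could have been meant per fraction. This stands as to intent. The 0.84 figure describes the null hypothesis as written, which is why the plan must name the scale.
- **Only 10.4 specifies a test.** 10.1 is a design summary and a statistician could work out the order. This is true, but 10.1 is current text giving a different margin for the same comparison, and the order should not need to be inferred.
- **The consequence is limited.** In the sensible order the test is stricter than either margin read per fraction, so false claims are not inflated; understated rectal power does no harm. Both points stand.
- **Accrual is 57, and nothing caps the analysis at 40.** If 50 to 52 were evaluable (a loss of about 9% to 12%, an assumption), the stated bladder inputs give 93.4% to 94.2%. But the power claim is made for 20 evaluable per arm, and 40 of 57 implies a planned loss of about 30%.

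**Conclusion.** The concern holds. Read literally, with fraction 3 minus fraction 2, the primary test in 10.4 excludes an excess of 0.84 Gy per fraction. That figure is undisclosed and differs from the 1 Gy in 10.1. The order that makes this so is not stated. On the inputs given, bladder power is 86.9%, about 7 points below the printed 94%, and rectal power is above 99.9% rather than 96%.

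This should be fixed before analysis. It is not a type I error problem in the sensible order: rejection is 2.5% at τ = 0.84 and 0.5% at τ = 1 for bladder. The costs are an overstated bladder power and a primary verdict that depends on which margin and scale a reader applies, as with an observed 0.40 Gy.

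The figures assume that the SD of the fraction 2 to 3 difference under mixed packing equals that under standard packing, and that there is no differential carryover. If carryover into fraction 3 differs by λ (after hydrogel minus after standard), the contrast becomes 2τ − λ. The documents give no value for λ. Over an illustrative −0.25 to +0.25 Gy, bladder power at τ = 0.12 runs from 65.2% to 91.6%, and rejection at τ = 0.84 from 0.7% to 7.1%.

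**What to change.** 1. Reconcile the margins in 10.1 and 10.4 into one δ, and say whether it applies to τ or to the contrast 2τ. The choice of value is the sponsor's.
2. Define diff as fraction 3 minus fraction 2 in both arms.
3. Match the test to the scale. If δ is on τ, compare (mean diffA − mean diffB)/2, with half the two-sample standard error, with δ. If δ is on the contrast, compare the full contrast with δ and state the per-fraction equivalent δ/2.
4. Restate power for bladder and rectum separately, with an explicit assumed τ and the equal-SD and no-carryover assumptions.

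Step 1 must come first. Halving the contrast while keeping 1.68 would by itself move the bladder cut-off from an observed 0.34 to 1.18 Gy.

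The cost is a few lines in 10.1, 10.3.2, 10.4 and 10.6 and a rerun of the power calculation, with no new data. Whether more than 20 evaluable participants per arm are needed depends on the margin and scale chosen.

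### The 1.68 margin applied to the rectum is built from bladder figures alone, and the stated 96% rectal power does not belong to it

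*Combined protocol and SAP*

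**What the plan says.** Section 10.4 (Sample Size and Accrual) takes the fraction 2 to fraction 3 change in D2cc from 51 patients treated with standard packing at one of the two sites. It reports a "mean (standard deviation) of 0.12 (1.56) and 0.10 (0.92) D2cc for the difference for bladder and rectal dosimetry, respectively". It then introduces the margin with "Based upon these measurements and clinical judgement" and shows it as a sum: "a non-inferiority margin of δ =(0.12+1.56=1.68) was chosen for this study".

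The hypothesis that follows uses "δ =1.68, *each* for bladder and rectal", tested "with a one-sided 2.5% level t-test". With 20 evaluable participants per arm, the plan states 94% power for a true difference of 0.12 and an SD of 1.56, which are the bladder values. For the other organ it adds only: "Power is 96% if one uses the estimates for rectal dosimetry". No rectal margin is derived in section 10.4. Section 10.1 (Design) gives a different margin, 1 Gy, for both organs.

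**The concern.** Rectal D2cc is one of two primary endpoints, and section 2.1 names displacement of the rectum as a purpose of packing. The rectal margin is therefore one of the two numbers that decide the trial. As written, it is the bladder's mean plus the bladder's SD, although the rectal mean and SD stand beside them and the rectal SD is much smaller (0.92 against 1.56).

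The rectal power figure raises a second doubt. With the same margin and a smaller SD, rectal power should be far above bladder power, not two points above it. A figure of 96% suggests that the calculation used a different rectal margin from the one in the hypothesis. If so, the plan holds two rectal decision limits, one written and one implied, and the rectal conclusion could depend on which is used.

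**Working it through.** **Inputs, all from section 10.4 unless noted.** Bladder mean (SD) of the difference 0.12 (1.56); rectum 0.10 (0.92); historical n = 51; 20 evaluable per arm; one-sided 2.5% two-sample t-test; margin 1.68 for each organ. Section 10.1: margin 1 Gy.

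**Step 1: are the SDs read correctly?** The 95% CI width for a mean is 2 × t(50) × SD/√51. This gives 0.88 for bladder and 0.52 for rectum. The plan states 0.9 and 0.5, so the SDs are as read.

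**Step 2: origin of the margin.** Bladder: 0.12 + 1.56 = 1.68. Rectum by the same sum: 0.10 + 0.92 = 1.02. Ratio: 1.68/1.02 = 1.65. In rectal SDs: 1.68/0.92 = 1.83, against 1.02/0.92 = 1.11.

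**Step 3: power.** Exact noncentral t with df = 38 and noncentrality (margin - true difference)/(SD × √(2/20)). The standard error is 1.56 × 0.3162 = 0.493 for bladder and 0.92 × 0.3162 = 0.291 for rectum. Section 10.4 does not define the direction of diff_A and diff_B, so both signs of the true difference are shown. A plus sign lies toward the margin as H0 is written.

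| Organ | Margin | Power, plus sign | Power, minus sign | Stated |
|---|---|---|---|---|
| Bladder (±0.12) | 1.68 | 86.9% | 94.5% | 94% |
| Bladder (±0.12) | 1.00 | 41.3% | 60.0% | 94% |
| Rectum (±0.10) | 1.68 | 99.96% | about 100% | 96% |
| Rectum (±0.10) | 1.02 | 86.9% | 96.3% | 96% |
| Rectum (±0.10) | 1.00 | 85.4% | 95.8% | 96% |

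- The stated 94% for bladder is reproduced at 1.68 with the minus sign: (1.68 + 0.12)/0.493 = 3.65, giving 94.5%.
- The stated 96% for rectum is not reproduced at 1.68 with either sign: (1.68 - 0.10)/0.291 = 5.43, giving 99.96%.
- With the minus sign, any rectal margin from about 0.99 to 1.03 rounds to 96%. With the plus sign the margin would have to be about 1.21, still well below 1.68.
- Multiplying the rectal SD by √2 brings the 1.68 margin to 96.3%, but the same change takes bladder power to 58.7%. It does not explain the pair.

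The pair of 94% and 96% is therefore matched by 1.68 for bladder with about 1.0 for rectum, under the minus sign. A common 1 Gy fails on bladder, and a common 1.68 fails on rectum.

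**Step 4: what the choice does.** With SD 0.92 and 20 per arm, the largest observed rectal contrast that passes is the margin less 2.024 × 0.291 = 0.59. That is 1.09 at a margin of 1.68 and 0.43 at 1.02. If the true rectal contrast is 1.02, the chance of declaring non-inferiority is 59.9% with the 1.68 margin and 2.5% with 1.02. If it is 1.2, the 1.68 test still passes 36% of the time.

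**The case against.** The strongest answer is that the plan applies 1.68 to both organs in so many words and cites clinical judgement. A margin is a tolerable excess in Gy. It need not scale with an organ's variability, and one common limit can be a deliberate choice. The plan nowhere states a rule of mean plus one SD per organ; that is inferred from a single sum. This stands, and it limits what can be claimed.

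A reader might infer that the rectal limit is simply 65% too wide and that 1.02 is the right one. The documents do not support that. The 65% is the distance from the value that the bladder recipe implies, and they give no clinical rationale for that recipe in either organ. For the same reason, the 60% against 2.5% is an error rate only if 1.02 is the limit of acceptability. Under the margin as written, a true contrast of 1.02 counts as non-inferior.

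A reader might also infer that only 1.02 reproduces the stated 96%. It does not stand alone: the 1 Gy of section 10.1 gives 95.8%. Both matches need the true difference at -0.10. Read literally, with the positive historical means and H0 as written, 1.02 gives 86.9%. The power figure cannot show which rectal margin was intended.

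None of this makes 1.68 agree with 96%. Clinical judgement could justify a common margin, but section 10.4 gives no rectal reasoning, and the power it reports belongs to a smaller margin. Choosing 1 Gy for both organs would settle the rectal question, but would leave the bladder with 41% to 60% power.

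**Conclusion.** The point holds in a limited form. Two things are established from section 10.4 alone: the rectal margin of 1.68 contains no rectal figure, and the stated 96% rectal power is wrong for that margin, which gives 99.96% or more. The 96% fits a rectal margin near 1.0. Whether that is 1.02 or 1 Gy cannot be told from the documents, and neither is shown to be the correct limit.

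The size is a factor of 1.65 between the written rectal margin and the one that the plan's recipe implies, with the effect on the rectal decision shown above. The power figures assume 20 evaluable per arm, the historical SDs and the stated one-sided 2.5% level. The factor of 1.65 does not depend on the scale of the contrast. That scale also needs stating: if each difference is period 2 minus period 1 and there is no carryover, the arm contrast is twice the packing effect per fraction.

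**What to change.** Amend section 10.4 before analysis:

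1. State one margin for bladder and one for rectum, each with its own justification. The recipe already used implies 1.68 and 1.02. Write the hypothesis with a separate δ for each organ.
2. Reconcile these values with the 1 Gy in section 10.1.
3. Define the direction of diff_A and diff_B, and state the sign of the assumed true difference.
4. Restate both powers at 20 per arm. For margins of 1.68 and 1.02 they are bladder 86.9% (+0.12) or 94.5% (-0.12), and rectum 86.9% (+0.10) or 96.3% (-0.10).
5. If 1.68 is deliberately kept for the rectum, give a rectal rationale and replace 96% with above 99.9%.

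The cost is wording in sections 10.1 and 10.4. Margins of 1.68 and 1.02 need no added patients or procedures, though the powers to be reported may fall to 86.9%. A common 1 Gy would not be free, because 20 per arm then gives bladder power of at most 60%. The change should precede any look at outcome data, since a margin altered afterwards loses credibility.

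### The stated powers of 94% (bladder) and 96% (rectum) do not follow from the inputs printed in section 10.4

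*Combined protocol and SAP*

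**What the plan says.** Section 10.4 bases the primary comparison on fractions 2 and 3. Each participant contributes a between-fraction difference in D2cc, and the two arms' mean differences are compared by a two-sample test. The null is that the arm A mean minus the arm B mean is at least the margin, tested separately "for bladder and rectal, with a one-sided 2.5% level t-test".

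The planning data are 51 UVA patients treated with standard packing, which "resulted in a mean (standard deviation) of 0.12 (1.56) and 0.10 (0.92) D2cc for the difference for bladder and rectal dosimetry". The margin is the bladder mean plus the bladder SD ("0.12+1.56=1.68) was chosen for this study") and is applied to both organs.

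With 20 evaluable per arm the design "achieves 94% power to detect non-inferiority using a one-sided t-test when the margin of non-inferiority is 1.68", where "the true difference between the means and the reference (standard) value is 0.12" and the SD is 1.56. For the other organ: "Power is 96% if one uses the estimates for rectal dosimetry".

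On direction, the text says only that the two arm quantities "denote the differences between fractions". Section 10.1 gives another margin, "for rectum and bladder by more than a non-inferiority margin of δ =1 Gy".

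**The concern.** Both organs share the sample size, the test, the significance level and the margin, and their assumed differences are almost equal (0.12 and 0.10). The rectal SD is 41% smaller (1 − 0.92/1.56). Rectal power should therefore be far above bladder power, not two points above it. That alone suggests that the two figures were not both computed with 1.68.

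Two things are at stake. First, the justification for 20 per arm cannot be reproduced, and on the literal reading the bladder type II error is 13.1% rather than 6%. Second, the rectal figure hints at a margin near 1.0, while section 10.4 prints 1.68. A rectal upper confidence limit between about 1.0 and 1.68 would pass under one margin and fail under the other, so the criterion for the primary test is in doubt as well as the power.

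**Working it through.** **Inputs.** From section 10.4: n = 20 per arm; one-sided α = 0.025; margin δ = 1.68 for each organ; bladder difference 0.12, SD 1.56; rectal difference 0.10, SD 0.92. Equal allocation is from section 10.2. As a check on the SDs, the 95% CI widths that they imply for 51 patients are 0.88 and 0.52, which match the printed 0.9 and 0.5.

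**Formula.** Power = P(T > t₀.₉₇₅,₃₈), where T is noncentral t with 38 df and ncp = (δ − d) / (SD·√(2/20)). The null is a contrast at or above δ, so a positive d lies toward the margin.

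**Printed inputs, d positive**
- Bladder: SE = 1.56 × 0.3162 = 0.4933; ncp = 1.56/0.4933 = 3.162; power **86.9%** (normal approximation 88.5%). Stated: 94%.
- Rectum: SE = 0.92 × 0.3162 = 0.2909; ncp = 1.58/0.2909 = 5.431; power **99.96%**. Stated: 96%.

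**Which inputs give the stated figures?**

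| Organ | δ | d | ncp | Power |
|---|---|---|---|---|
| Bladder | 1.68 | +0.12 | 3.162 | 86.9% |
| Bladder | 1.68 | 0 | 3.406 | 91.3% |
| Bladder | 1.68 | −0.12 | 3.649 | 94.5% (0.9447) |
| Rectum | 1.68 | +0.10 | 5.431 | 99.96% |
| Rectum | 1.68 | 0 | 5.775 | 99.99% |
| Rectum | 1.68 | −0.10 | 6.118 | >99.99% |
| Rectum | 1.02 | +0.10 | 3.162 | 86.9% |
| Rectum | 1.02 | −0.10 | 3.850 | 96.3% |
| Rectum | 1.00 | −0.10 | 3.781 | 95.8% |

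Here 1.02 = 0.10 + 0.92 is the plan's own mean-plus-SD rule applied to the rectum, and 1.00 is the margin in section 10.1. The stated pair appears with negative differences and a rectal margin of 1.02 or 1.00. The two margins cannot be told apart, since both round to 96%.

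**Other explanations tried**
- One-sided 5%, δ = 1.68, positive d: bladder 92.8%, rectum 99.99%. This does not give the pair.
- Mean-plus-SD margins with positive d: (δ − d)/SD = 1 for either organ, so ncp = 1/√(2/20) = 3.162 and both powers are 86.9%. Two different figures cannot arise.
- The per-fraction (half-difference) estimate with δ = 1 and positive d: bladder ncp = 0.88/(0.4933/2) = 3.568, power 93.5%. Rectal ncp = 0.90/(0.2909/2) = 6.187, power above 99.99%. Again, not the pair.

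**Direction and scale.** Section 6.1 gives arm A standard packing at fraction 2 and hydrogel at fraction 3; arm B has the reverse. With fraction 3 minus fraction 2, the arm A mean is (effect + period) and the arm B mean is (−effect + period). The contrast is then twice the packing effect, absent carryover. A positive value means more dose with hydrogel, and 1.68 corresponds to 1.68/2 = 0.84 Gy per fraction. If the subtraction is reversed, a positive contrast favours hydrogel and the one-sided null tests the wrong direction. The text does not say which applies.

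**Sample size for 94% with d = +0.12, δ = 1.68.** 25 per arm gives 93.4%; 26 per arm gives 94.2%.

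**The case against.** The strongest reply is that the bladder arithmetic may not be wrong. Power at −0.12 is 0.9447, which rounds to 94%, and −0.10 with a margin of 1.02 rounds to 96%. One recipe therefore reproduces both figures to the printed precision, and the fault is unreported inputs rather than miscalculation. This is a likely account of what was done. It does not rescue the text: section 10.4 prints 0.12 without a minus sign and 1.68 for both organs.

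A second point has more force. The 0.12 comes from patients who had standard packing at both fractions, so it is a period difference and not a packing effect. A common period difference cancels in the arm contrast. If the packings are equivalent the true contrast is zero and bladder power is 91.3%, about 3 points below the stated figure. So 86.9% is what the printed inputs give, and not necessarily the best planning figure. The same point counts against the favourable sign: data under standard packing alone give no support for assuming a hydrogel benefit.

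Third, section 10.4 names no target power, 87% would satisfy most readers, and the rectal error at 1.68 is conservative. This limits the consequence. It leaves open which rectal margin is meant.

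**Conclusion.** The concern holds. Under the test, significance level, margin and sample size printed in section 10.4, power is 86.9% for the bladder and 99.96% for the rectum when the assumed difference lies toward the margin, against 94% and 96% stated. The bladder result depends on the sign (86.9%, 91.3% or 94.5%), which the text leaves open. The rectal conclusion does not depend on it: at 1.68 every sign gives more than 99.9%, so at least one printed statement is wrong.

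The consequence is moderate. If 1.68 on the printed contrast is the intended margin for both organs, the design remains adequately powered and only the reported figures need correcting. If the rectal margin was really 1.02, the statement of a common 1.68 is the error, and rectal power toward the margin is 86.9%. If the 1 Gy of section 10.1 applies to the printed contrast, power toward the margin is 41.3% for the bladder and 85.4% for the rectum. The margin therefore has to be settled before either power can be interpreted. All figures assume the planning SDs and 20 evaluable per arm.

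**What to change.** In section 10.4:

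1. Define each arm's difference as fraction 3 minus fraction 2, so that a positive arm A minus arm B contrast means more dose with hydrogel.
2. State the assumed true contrast with its sign, and why. Zero is the natural value if the packings are taken as equivalent; a value favouring hydrogel needs its own justification.
3. State the margin for the bladder and for the rectum, and whether it applies to the contrast or per fraction (1.68 on the contrast is 0.84 Gy per fraction; 1 Gy per fraction is 2 Gy on the contrast).
4. Reconcile this with the 1 Gy in section 10.1.
5. Restate both powers. For 1.68 on the contrast in both organs: 87% (bladder) and above 99.9% (rectum) with +0.12 and +0.10; 91% and above 99.9% with zero.

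The cost is a few sentences in section 10.4 and one figure in section 10.1. No extra participants are needed if 1.68 on the contrast is kept. Holding 94% for the bladder with the difference toward the margin would take 26 evaluable per arm (52 in all) instead of 20. The margin should be settled before the dosimetry is analysed, since it decides the primary test.

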6 STUDY INTERVENTION

6.1 Description of Study Intervention(s)

Participants will be assigned to Arm A or Arm B, as described in section 4.1 and Figure 1. Fraction 1 for all participants (both Arms) will receiving standard of care packing. During fractions 2-5 of brachytherapy, participants will have vaginal packing alternating between the BrachyGel Vaginal Hydrogel Packing System and standard of care vaginal packing, strategy which will include gauze vaginal packing or rectal retractor.

For Arm A of the study, the BrachyGel Packing System will be used during fractions 3 and 5. Standard packing will be used for fractions 1, 2 and 4.

For Arm B of the study, the BrachyGel Packing System will be used during fractions 2 and 4. Standard packing will be used for fractions 1, 3 and 5.

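### Section 10.4 uses the standard-packing change between fractions (0.12 Gy) as the true packing difference and as part of the margin, and its stated 94% and 96% power do not follow from the printed inputs

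*Combined protocol and SAP*

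**What the plan says.** Section 10.4 bases the primary test on each participant's change in D2cc between fractions 2 and 3. It compares the mean change in Arm A with that in Arm B, and says that diffA and diffB "denote the differences between fractions". The sequences are in section 6.1: "For Arm A of the study, the BrachyGel Packing System will be used during fractions 3 and 5", and "For Arm B of the study, the BrachyGel Packing System will be used during fractions 2 and 4". So at fractions 2 and 3 Arm A has standard then BrachyGel, and Arm B has BrachyGel then standard.

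The planning figures come from "Data from 51 patients treated at UVA with fraction 2 and 3 information". These patients, "with standard packing resulted in a mean (standard deviation) of 0.12 (1.56) and 0.10 (0.92) D2cc for the difference", for bladder and rectum respectively. From those figures and clinical judgement, "a non-inferiority margin of δ =(0.12+1.56=1.68) was chosen for this study", and 10.4 applies that margin to each organ.

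For the sample size, 10.4 assumes that "the true difference between the means and the reference (standard) value is 0.12", with SD 1.56, 20 evaluable participants per arm and a one-sided 2.5% t-test. It states 94% power, and 96% on the rectal estimates. Section 10.1 gives a margin of 1 Gy for the same comparison.

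**The concern.** The 51 patients had the same packing at both fractions, so their mean change holds no packing difference. It can only reflect change from fraction 2 to fraction 3, or chance. A crossover with opposite sequences is built to remove such a change. Using it as the assumed packing effect, and again as a component of the margin, puts a quantity unrelated to BrachyGel into the decision threshold and the planning alternative.

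The margin decides whether the trial succeeds, and the power statement is the stated justification for 20 evaluable participants per arm. If the power does not follow from its own inputs, a reader cannot tell what the trial was designed to detect, or under which margin.

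**Working it through.** **1. The period effect cancels.** Let π be the change from fraction 2 to 3 that both arms share, and τ the packing effect (BrachyGel minus standard). Section 10.4 gives no direction for the difference. Take fraction 3 minus fraction 2, under which a large positive contrast is unfavourable to BrachyGel, as the hypotheses require.

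- Arm A: E[diffA] = π + τ
- Arm B: E[diffB] = π − τ
- Contrast: E[diffA] − E[diffB] = 2τ

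Equal packings give 0 whatever π is. In simulation with τ = 0, margin 1.68 and SD 1.56, π = 0, 0.12 and 1.0 all gave power of about 91%. The contrast is twice the packing effect, so 1.68 on it is 1.68/2 = 0.84 Gy per fraction.

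**2. The pilot figures.** The 95% CI widths in 10.4 (0.9 and 0.5) reproduce: 2 × 2.009 × 1.56/√51 = 0.88 and 2 × 2.009 × 0.92/√51 = 0.52. So 1.56 and 0.92 are SDs of individual changes. The standard error of the bladder mean is 1.56/√51 = 0.218, so 0.12 is 0.12/0.218 = 0.55 standard errors from zero. In the margin, 0.12/1.56 = 7.7%.

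**3. Power.** Two-sample non-inferiority t-test, 20 per arm, df 38, one-sided 2.5%, with noncentrality (margin − true contrast)/(SD × √(2/20)). The denominator is 1.56 × 0.3162 = 0.4933 for bladder and 0.92 × 0.3162 = 0.2909 for rectum.

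| Case | Margin | True contrast | SD | Noncentrality | Power |
|---|---|---|---|---|---|
| Bladder, printed inputs (plan: 94%) | 1.68 | 0.12 | 1.56 | 3.16 | 86.9% |
| Bladder, equal packings | 1.68 | 0 | 1.56 | 3.41 | 91.3% |
| Bladder, equal packings, drift out of margin | 1.56 | 0 | 1.56 | 3.16 | 86.9% |
| Bladder, drift in BrachyGel's favour | 1.68 | −0.12 | 1.56 | 3.65 | 94.5% |
| Bladder, packing effect 0.12 Gy (contrast 0.24) | 1.68 | 0.24 | 1.56 | 2.92 | 81.2% |
| Rectum, margin as set (plan: 96%) | 1.68 | 0.10 | 0.92 | 5.43 | >99.9% |
| Rectum, margin 0.10 + 0.92 | 1.02 | 0.10 | 0.92 | 3.16 | 86.9% |
| Rectum, same margin, drift in BrachyGel's favour | 1.02 | −0.10 | 0.92 | 3.85 | 96.3% |
| Bladder, section 10.1 margin put on the contrast | 1.00 | 0 | 1.56 | 2.03 | 50.6% |

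The normal approximation gives 88.5% for the printed bladder inputs, so the choice of t or z does not explain 94%. By the t-test, 94% needs 26 per arm on the printed inputs, or 23 per arm at contrast 0 with margin 1.68.

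**4. Can the stated figures be recovered?** At the stated alpha, the variants tried match both figures closely only with the drift entered in BrachyGel's favour, and the rectal figure also needs a margin of 1.02, which 10.4 does not set. At one-sided 5%, the printed bladder inputs give 92.8% (t) or 93.5% (z), near 94%. That contradicts the stated level and still does not give 96% for the rectum (92.8% with margin 1.02, above 99.9% with 1.68). A contrast of 0 at one-sided 5% gives 95.5% and, with a rectal margin of 1.02, 96.4%, but it departs from both the stated alpha and the stated 0.12.

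**The case against.** The strongest reply is that planning at a small unfavourable difference is legitimate in a non-inferiority trial and more cautious than planning at 0. That stands. Zero is not compulsory, but a non-zero value needs a reason tied to packing, and 0.12 has none. Section 10.4 also cites clinical judgement for the margin, though it names no tolerable mean change in D2cc.

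A reader might infer that the double use of 0.12 causes the shortfall from 94%. The figures do not support that. The printed inputs already give 86.9%. Removing 0.12 from both places leaves the distance to the margin unchanged (1.68 − 0.12 = 1.56 − 0) and so leaves power at 86.9%. Setting only the true contrast to 0 raises power to 91.3%. The shortfall is a separate failure to reproduce.

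A reader might also multiply 1.68 Gy by five fractions and set 8.4 Gy against the 65 and 75 Gy rectal bands in section 2.3.1. That does not hold. On the contrast, 1.68 is 0.84 Gy per fraction, participants receive BrachyGel in two fractions, and the margin was built from bladder data.

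Finally, the drift would stay in if diffA and diffB each meant hydrogel minus standard. Section 10.4 does not say that.

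**Conclusion.** The point holds on two counts. First, 0.12 Gy is a standard-packing period difference. It cancels from μdiffA − μdiffB, carries no information on BrachyGel, and widens the bladder-derived margin by 7.7%. Second, the stated powers do not follow from the stated inputs: 86.9% instead of 94% for bladder, and above 99.9% instead of 96% for rectum at the margin set for each organ. That the drift was credited to BrachyGel is an inference from the close match (94.5% and 96.3%); the documents do not show how the figures were produced.

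The loss of bladder power is moderate if 1.68 stands: 91.3% at equal packings. The open margin matters more. Read as 1 Gy on the contrast, section 10.1 leaves 50.6% bladder power. Read as 1 Gy of packing effect, it is 2 Gy on the contrast and gives 97.7%.

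These results assume a period effect common to both arms, no carryover, SD 1.56 or 0.92 in both arms although it was observed under standard packing only, and 20 evaluable participants per arm.

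**What to change.** In section 10.4:

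- Stop using 0.12 (or 0.10) as the packing difference or as a margin component.
- Define the direction of diffA and diffB. State the planning value on the contrast scale: 0 for equal packings, or another value with a reason. Note that the contrast is twice the packing effect.
- State the margin on the same scale, with its clinical rationale.
- Restate bladder and rectal power for the margin actually used, at one-sided 2.5%.

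Reconcile 1.68 Gy in 10.4 with 1 Gy in 10.1, saying whether each refers to the contrast or to the per-fraction packing effect. If 1 Gy on the contrast is kept, state that bladder power at 20 per arm is about 51%.

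The cost is wording if 1.68 stands and 91.3% is accepted. Keeping 94% at contrast 0 needs 23 per arm, or 46 evaluable. At the evaluable fraction implied by 10.4 (40/57 = 70%), that is 46 × 57/40 = 65.6, so about 66 accrued instead of 57. A smaller margin on the contrast would also affect enrolment, which is a trade-off for the sponsor to decide.
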